6.2. Secondary and Exploratory Endpoints

6.2.1. Secondary Binary Endpoints

The EASI-75 response at Week 16 is the binary secondary efficacy endpoint in Part 1 DB phase. The analysis of the binary secondary endpoint will be based on Estimand E1 accounting for the intercurrent events using the FAS (Section 2.2.2, Appendix 3). This corresponds to the Estimand E1 including only the pre-intercurrent-event data (Appendix 3). For the secondary analysis, the normal approximation for the difference in binomial proportions adjusting for the actual stratification factor of baseline IGA (3 vs 4) via the CMH approach (Section 5.2.1.1) will be used. The baseline IGA is from the clinical database will be used as the actual stratification factor (Section 3.4.1). This CMH approach will be used to estimate the treatment difference in response rates of etrasimod 2 mg QD versus placebo and to generate 95% CI for the EASI-75 response rate difference at Week 16 along with the 2-sided p-value (Section 5.2.1.1). Missing values will be handled by setting the EASI-75

^[2] Only reasons with at least one participant in any group will be summarized.

response value to non-response, MR=NR (Section 5.3). This is the secondary analysis for EASI-75 response at Week 16.

Analysis of EASI-75 response at other visits prior to Week 16 (ie, exploratory endpoints) will also be analyzed using the same CMH method based on the Estimand E1 including pre-intercurrent-event data on the FAS.

Supportive analyses for EASI-75 for visits up to Week 16 will also be performed under the Estimand E1a using FAS (including all data). The same CMH approach adjusting to actual stratification factor (Section 3.4.1) will also be used. These analyses are to support the secondary analysis of estimating the treatment difference in response rates of etrasimod 2 mg QD versus placebo for EASI-75 at Week 16.

6.2.2. Exploratory Binary Endpoints

Analysis of other exploratory endpoints for Part 1 DB phase: \geq 4-point reduction from baseline in PP-NRS at all visits up to Week 16 (analyzed only for participants with baseline PP-NRS \geq 4), \geq 4-point reduction from baseline in Skin Pain NRS at all visits up to Week 16 (analyzed only for participants with baseline Skin Pain NRS \geq 4), EASI-90 response at all visits up to Week 16, and \geq 4-point reduction from baseline in POEM at Week 16 (analyzed only for participants with baseline POEM \geq 4), will also be analyzed using the same CMH method based on the Estimand E1 including pre-intercurrent-event data on the FAS. No supportive analyses are performed for these exploratory endpoints.

6.2.3. Secondary Continuous Endpoint (Repeated Visits)

The percent change from baseline in EASI at Week 16 is the continuous secondary efficacy endpoint in Part 1 DB phase. The analysis of the continuous secondary endpoint will be based on Estimand E2 accounting for the intercurrent events using the FAS (Section 2.2.2, Appendix 3). This corresponds to the Estimand E2 including only the pre-intercurrent-event data (Appendix 3). For this secondary analysis, the JTC method will be used to analyze percent change from baseline in EASI score at Week 16 (Section 5.2.2.1 for details on how to handle intercurrent events). This analysis will provide the LSM of the treatment group, the LSM of the treatment difference (Etrasimod 2 mg QD versus Placebo) in percent change from baseline in EASI score at Week 16, 95% CI and the 2-sided p-value from the Rubin's rules to estimate the treatment difference of etrasimod 2 mg QD versus placebo of this continuous secondary endpoint (Section 5.2.2.1).

Analysis results of percent change from baseline in EASI score at other visits prior to Week 16 (ie, exploratory endpoints) will also be obtained from the same JTC method performed above under the same Estimand E2 using the FAS.

A supportive analysis will be performed for percent change from baseline in EASI score at visits up to Week 16 under the Estimand E2a regardless of intercurrent events using the FAS (Section 2.2.3, Appendix 3). The MMRM model including all available data up to Week 16 will be used (Section 5.2.2.2). This analysis is to support the secondary analysis of estimating the treatment difference of etrasimod 2 mg QD versus placebo for percent change from baseline in EASI at Week 16.

6.2.4. Other Exploratory Binary Endpoints

For Part 1 OLE, binary exploratory endpoints at all visits from Week 20 up to Week 68 (eg, EASI-75 response), will be analyzed at each visit, including all available data on the FAS (since intercurrent events are not considered in this Part 1 OLE phase), using the normal approximation for the difference in binomial proportions adjusting for the actual stratification factor of baseline IGA (3 vs 4) via the CMH approach (Section 5.2.1.1). The baseline IGA from the clinical database will be used as the actual stratification factor (Section 3.4.1). This CMH approach will provide treatment comparison of Etrasimod 2 mg QD versus Placebo → Etrasimod 2 mg QD and generate 95% CI for the EASI-75 response rate difference at this visit along with the 2-sided p-value (Section 5.2.1.1). Missing values will be handled by setting the EASI-75 response value to non-response, MR=NR (Section 5.3).

This CMH approach will also be applied to IGA of clear (0) or almost clear (1) response, \geq 4-point reduction from baseline in PP-NRS score (analyzed only for participants with baseline PP-NRS \geq 4), \geq 4-point reduction from baseline in Skin Pain NRS score (analyzed only for participants with baseline Skin Pain NRS \geq 4), and EASI-90 response, at all visits from Week 20 up to Week 68.

For Part 2 OL Safety, binary exploratory endpoints at all visits will only be descriptively summarized for the single treatment group of Etrasimod 2 mg QD using only observed values on the FAS (since intercurrent events are not considered in this Part 2 OL Safety phase). Therefore, missing responses will not be imputed using the MR=NR in this Part 2 OL Safety phase (Section 5.3). This approach is applicable to EASI-75 response, IGA of clear (0) or almost clear (1) response, \geq 4-point reduction from baseline in PP-NRS score (analyzed only for participants with baseline PP-NRS \geq 4), \geq 4-point reduction from baseline in Skin Pain NRS score (analyzed only for participants with baseline Skin Pain NRS \geq 4), and EASI-90 response, at all visits from Week 4 to Week 52. The baseline is the pre-dose Day 1 of Part 2 OL Safety phase (Section 3.4).

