4.1. Full Analysis Sets

The full analysis set (FAS) will include all participants who are randomized to the study irrespective of whether they receive any dose of study intervention (ie, etrasimod or placebo). Participants will be analyzed in the treatment groups as they are randomized. If a participant DMB02-GSOP-RF02 7.0 Statistical Analysis Plan Template 31-Jan-2022

is treated but not randomized, then this participant will be excluded from the FAS. A narrative will be provided for this participant in the clinical study report (CSR). For a participant who is randomized but not treated, for Part 1 DB and OLE, baseline value for efficacy and safety endpoints is defined as the value obtained on the date of randomization as Day 1 or prior (if the Day 1 value is not available) in the Part 1 DB phase in the analyses.

In general, the analysis population for analyzing all efficacy endpoints in this study is defined by the complete FAS. However, there are some exceptions: some efficacy endpoints, defined by specific point reduction from baseline, require the inclusion of only participants who meet a baseline threshold in the analysis set to allow them the potential to respond in these efficacy endpoints. The details of these exceptions are provided below. Therefore, when considering analyzing an efficacy endpoint under an estimand, it is important to consider these exceptions.

FAS for Specific Efficacy Endpoints

The following four binary efficacy endpoints will only be analyzed including participants who meet the specific baseline threshold. This is to ensure that only participants with the potential to respond at a post-baseline visit are included in the analyses.

- IGA response defined as clear (0) or almost clear (1) on a 5-point scale and a reduction of ≥2 points from baseline (Appendix 2.2.1): Only participants with baseline IGA ≥2 in the FAS are included in all analyses of IGA response, knowing that only participants with baseline IGA ≥3 are eligible to enroll in this study.
- ≥4-point reduction in PP-NRS score from baseline (Appendix 2.2.4): Only participants with baseline PP-NRS ≥4 in the FAS are included in all analyses of this endpoint.
- ≥4-point reduction in Skin Pain NRS score from baseline (Appendix 2.2.5): Only participants with baseline Skin Pain NRS ≥4 in the FAS are included in all analyses of this endpoint.

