4.2. Safety Analysis Set

The safety analysis set (SAS) will include all participants who are randomized and receive at least one dose of the study treatment (ie, etrasimod or placebo). Participants will be analyzed in the treatment groups as they receive. If a participant is treated but not randomized, then the participant will be excluded from SAS. A narrative will be provided for this participant in the CSR. The SAS will be the analysis set for safety analyses in all phases of the study.

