5.2. General Methods

In Part 1 DB, as all participants randomized to treatment groups of etrasimod 2 mg QD and placebo will switch to open-label treatment of etrasimod 2 mg QD at Week 16, the treatment labels used for reporting DB visits up to Week 16 will be "Etrasimod 2 mg QD" and "Placebo" respectively. At the end of Part 1 OLE, when reporting OLE visits from Week 20 through Week 68, the treatment labels used will be "Etrasimod 2 mg QD" and "Placebo → Etrasimod 2 mg QD" respectively to differentiate these two treatment groups.

For Part 1 DB analyses up to Week 16, the following treatment comparison will be made at each timepoint, where applicable:

• Etrasimod 2 mg QD vs. Placebo.

The primary efficacy comparison for the primary endpoint of IGA response at Week 16 will be between etrasimod 2 mg QD and placebo. For analyses after Week 16 from Week 20 through Week 68 (Part 1 OLE phase), the following treatment comparison will be made at each timepoint,

• Etrasimod 2 mg QD vs. Placebo \rightarrow Etrasimod 2 mg QD.

For Part 2 OL Safety phase, there will only be one treatment group of etrasimod 2 mg QD, the label will be "Etrasimod 2 mg QD". There is no treatment comparison in Part 2. There will be no pooling of efficacy and safety data of Part 1 and Part 2 in this study.

Descriptive Summaries

In general, the data for all continuous endpoints will be summarized by treatment group and by timepoint in tables containing descriptive statistics (N as the number of participants evaluable for the endpoint at the timepoint, mean, standard deviation, standard error of the mean, minimum, 1^{st} , 2^{nd} (ie, median) and 3^{rd} quartiles and maximum) for actual and change from baseline (or percent change from baseline) values for those endpoints measured at baseline. In case when N=1 (ie, only one participant is available/evaluable for summary), standard deviation and standard error will be reported as "NA" (not applicable) while the remaining statistical parameters will have the same value as the mean. The data for all response-type binary endpoints will be summarized by treatment group and by timepoint in tables showing descriptive statistics: N, n (ie, number of responders), response rate, standard error (SE) of the response rate, and 95% confidence interval (CI) based on normal approximation, all expressed in %. If \hat{p} is the estimated response rate, then the 95% CI is calculated as:

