In Part 1 OLE phase, since no estimands are defined for (binary or continuous) efficacy endpoints, all observed data collected/assessed regardless of any prior intercurrent events will be included in deriving the efficacy endpoints at a visit. If the binary efficacy endpoint at any visit has missing value, it will be handled by setting the binary efficacy endpoint to non-response. This method of handling missing binary efficacy endpoint is known as missing response as non-response (MR=NR), which is similar to using Estimand E1a (treatment policy estimand). If the continuous efficacy endpoint at any visit has missing, it will remain as missing, without imputation of missing value at this visit, which is similar to using Estimand E2a (treatment policy estimand). The same approach of including all observed data collected/assessed regardless of any prior intercurrent events will also be applicable to Part 2 OL Safety phase. Missing binary efficacy endpoints in Part 2 OL Safety phase will not be imputed as non-response, only observed values will be summarized.

In general, missing values in any (binary or continuous) efficacy endpoint will not be imputed when summarizing these endpoints using descriptive statistics. In addition, missing values for safety endpoints will not be imputed.

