c. Day of first open-label dose at Week 16 = Treatment switch day (ie, treatment switch day = treatment switch date – date of the first dose +1), where treatment switch date is taken from the Treatment Dosing CRF, as the start date in the first entry of the Treatment Dosing log for the period of Week 16 to Week 20.

Note that the upper limit of the Week 16 visit window and the lower limit of the Week 20 visit window are defined uniquely for each of the participants in the study regardless of which treatment group the participants are randomized to.

If treatment switch day (ie, day of first open-label etrasimod dose) falls between Day 99 and Day 126, then the upper limit of the Week 16 visit window is the smaller of treatment switch day or Day 126, and the lower limit of the Week 20 visit window is the smaller of treatment switch day+1 or Day 127.

In the unlikely case if treatment switch day < Day 99, > Day126, or missing (eg, discontinuation of study treatment or study prior to Week 16), then the upper limit of the Week 16 visit window will be set to Day 126 and the lower limit of the Week 20 visit window will be set to Day 127.

Table 9. Analysis Visit Windows for Part 2

Visit Label	Target Day ^a	Window Definition
Baseline	Day 1	Last non-missing assessment on or before Day 1 and prior to first dose of etrasimod
Week 4	Day 29	Day 2 to Day 42
Week 8	Day 57	Day 43 to Day 84
Week 16	Day 113	Day 85 to Day 140
Week 24	Day 169	Day 141 to Day 210
Week 36	Day 253	Day 211 to Day 280
Week 44	Day 309	Day 281 to Day 336
Week 52	Day 365	≥ Day 337

a. Target day is equal to the target week \times 7 days + 1 day.

For safety data collected for participants who complete the 2-week and 4-week follow-up visits (Weeks 70 and 72 in Part 1 OLE, Weeks 54 and 56 in Part 2 OL Safety phase), available safety data will be summarized for these nominal visits.

For 12-Lead ECG collected on Day 1 during first-dose cardiac monitoring, the labels for timepoints can be "Day 1 Predose", "Day 1 1HR Postdose" to "Day 1 4HR Postdose".

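### Part 1 OLE response rates at Weeks 20-68 are computed on everyone randomised with missing set to non-response, so placebo participants who never took etrasimod count as failures under an etrasimod label

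*SAP*

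**What the plan says.** **Who enters the OLE.** Protocol 4.1 offers the OLE as an option to participants who finish the double-blind (DB) period without a clinically significant safety concern. Protocol 7.1.1 requires discontinuation at Week 16 where there is such a concern. The Schedule of Activities (1.3.2) plans follow-up for those who decline or are ineligible.

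**How the SAP describes it.** SAP 5.2 writes that all participants randomised to either group "will switch to open-label treatment of etrasimod 2 mg QD at Week 16". It then gives two column labels for the OLE visits: the etrasimod arm keeps its DB label, and the placebo arm becomes Placebo → Etrasimod 2 mg QD. There is no label for a placebo participant who never switched.

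**Analysis sets.** SAP 4 defines two. The FAS contains "all participants who are randomized to the study irrespective of whether they receive any dose of study intervention". The safety set requires one dose of etrasimod or placebo, and "The SAS will be the analysis set for safety analyses in all phases of the study". Neither requires an open-label dose.

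**OLE binary efficacy.** SAP 6.2.4 and Table 7 apply the CMH method at each visit from Week 20 to Week 68, "including all available data on the FAS (since intercurrent events are not considered in this Part 1 OLE phase", and produce a 95% CI and p-value. On missing data in this phase, SAP 5.3 says: "If the binary efficacy endpoint at any visit has missing value, it will be handled by setting the binary efficacy endpoint to non-response".

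**Windows.** Appendix 2.1 makes observations from all visits eligible for allocation. Where the switch day is missing, "the upper limit of the Week 16 visit window will be set to Day 126 and the lower limit of the Week 20 visit window" to Day 127; the Week 20 window closes on Day 154.

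**Adverse events.** SAP 6.5.1 lists three displays: Part 1 DB, cumulative Part 1 DB+OLE, and Part 2. SAP 3.5 counts treatment-emergent events from the first dose of study treatment, which is placebo in the placebo arm.

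**The concern.** The OLE objectives are the long-term safety (primary) and efficacy (exploratory) of etrasimod. A reader will take a Week 52 rate in the Placebo → Etrasimod column as the response of people who moved from placebo to etrasimod. As planned, it is the response of everyone randomised to placebo, including those who left in the DB period, declined the extension or were stopped at Week 16. All of these are fixed as non-responders at visits they could not attend, on a drug they never took.

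Unequal non-entry between arms would also produce a difference, with a CI and p-value, that has nothing to do with response to treatment. None of this needs an unusual event such as sponsor termination; ordinary non-entry is enough.

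**Working it through.** **The plan's own figure.** The only precision figure concerns Week 16 (Protocol 9.5; 30 per group; 9% and 39%). The half-width is 1.96 × √(0.39×0.61/30 + 0.09×0.91/30) = 20.2%, as stated. The point made here does not affect it. No figure is given for OLE entry, so what follows is shown over a range.

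**1. OLE binary rates.** Let n = 30 be the placebo arm, d the share not entering, and p the response rate among entrants, with later drop-outs counted as non-responders. Non-entrants have no data from Week 24 on, so each is a non-response:

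displayed rate = p × (n − nd)/n = p(1 − d)

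| Non-entrants (d) | Entrants | p = 39% shows as | p = 50% shows as | p = 60% shows as |
|---|---|---|---|---|
| 3 (10%) | 27 | 35.1% | 45.0% | 54.0% |
| 6 (20%) | 24 | 31.2% | 40.0% | 48.0% |
| 9 (30%) | 21 | 27.3% | 35.0% | 42.0% |

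The values of d and p are assumptions; 39% is borrowed from the Week 16 planning rate for illustration.

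Effect on the comparison: with identical entrant rates of 39%, non-entry of 10% on etrasimod and 20% on placebo gives 35.1% against 31.2%, an apparent difference of 3.9 points.

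**2. Week 20.** The Week 16 visit is on Day 113 (±5), and participants are told not to dose before it, so the last blinded dose is about Day 112. Safety Follow-up 2 comes 28 days (±3) later: 112 + 28 = Day 140. With both tolerances the range is 107 + 28 − 3 = Day 132 to 117 + 28 + 3 = Day 148, all inside Day 127-154. The Schedule of Activities collects EASI, IGA, PP-NRS and Skin Pain NRS at that visit. A DB completer who did not enter therefore has an observed off-treatment value in the Week 20 window. It enters the CMH analysis, the observed-case summary and, for EASI, the MMRM, which SAP 6.2.5 says uses all data to Week 68. The sign of this error is not fixed: the participant is off study drug, and Protocol 6.9.3 no longer bars other treatments after the treatment period, with stated exceptions.

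**3. What is not affected in the same way.** SAP 5.2 and 5.3 keep descriptive response rates on observed data with evaluable denominators. The OLE continuous endpoints use an MMRM without imputation (SAP 6.2.5). Apart from the Week 20 values, neither counts a non-entrant as a failure.

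**4. Adverse events.** Let q be incidence in the placebo DB period and r incidence in the OLE among entrants, with DB events, entry and OLE events taken as independent.

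- OLE-onset events over the full safety set: r(1 − d). With r = 10% this shows 9.0%, 8.0% or 7.0% at d = 10%, 20% or 30%. This is always a dilution.
- Cumulative DB+OLE, as planned: 1 − (1 − q)(1 − r(1 − d)). With r = 10% and d = 20% it is 8.0% if q = 0, 12.6% if q = 5% and 17.2% if q = 10%. It equals r at q = 1 − 0.90/0.92 = 2.2% and exceeds r above that. With r = 30% and d = 20%, the break-even is q = 1 − 0.70/0.76 = 7.9%.

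The cumulative column can therefore lie on either side of the etrasimod-period incidence.

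**The case against.** **The full-set comparison is legitimate.** SAP 5.3 likens the OLE handling to the treatment-policy estimand, and keeping everyone randomised preserves the arm comparison. Restricting to entrants conditions on a post-randomisation event and removes etrasimod-arm participants who stopped in the DB period, some perhaps for adverse events. This stands as a reason to keep the full-set analysis. It does not make that analysis an estimate of response on open-label etrasimod.

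**Rates close to the entrant rate are already planned.** The observed-case summaries largely drop non-entrants. This limits the problem to the CMH tables, but those carry the CIs and p-values. Observed-case rates also drop entrants who later leave, including those discontinued at Week 32 for not reaching EASI-50, so they are no substitute.

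**SAP 5.2 only introduces column labels.** Appendix 2.1 does provide for a missing switch day, so the SAP knows that some will not switch. It still gives them no set and no label.

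**Follow-up visits are not named in the windowing rule.** True, and the intention may differ. But the rule covers all visits, and the separate nominal-visit provision is for safety data and names only Weeks 70 and 72 in Part 1.

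**Safety.** A reader might infer that OLE adverse-event incidence is biased downward, in the reassuring direction. The documents do not support that. The planned display is cumulative, DB-treated participants belong in its denominator, and placebo-period events push the figure up. SAP 4.2 also analyses participants by treatment received, which fits poorly with placing a placebo-only participant under an etrasimod label. What remains is that placebo and etrasimod periods are not separated.

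**Conclusion.** The point holds for the OLE binary CMH analyses. Displayed Placebo → Etrasimod rates shrink by (1 − d): a 50% entrant rate becomes 45-35% if 10-30% of the placebo arm does not enter. That range is an assumption, because the documents give no non-entry rate. From Week 24 on, the result follows directly from the FAS definition and the missing-data rule. At Week 20, as the windows are written, off-treatment follow-up values from DB completers who did not enter are reported as OLE data.

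It should not be read as saying that all OLE efficacy is diluted: the MMRM and observed-case summaries do not otherwise treat non-entrants as failures. For safety, the defect is a column that mixes periods and includes never-exposed participants. Its direction is open; dilution is certain only if OLE-onset events are divided by the full safety set.

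The affected efficacy endpoints are exploratory, and the Week 16 primary analysis is untouched. The change is still worth making before the Part 1 final analysis, because these tables describe long-term response to etrasimod.

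**What to change.** - **SAP 4:** define a Part 1 OLE set of randomised participants with at least one open-label dose, shown by DB arm.
- **SAP 6.2.4 and Table 7:** use it for the Weeks 20-68 binary response rates, with later drop-outs and Week 32 EASI-50 discontinuations still counted as non-responders. Keep the FAS comparison with missing as non-response as the supportive analysis of randomised sequences.
- **SAP 6.5:** use the OLE set as the denominator for any summary of events starting on or after the first open-label dose. Table 8 already assigns switch-day events to Week 20 onwards. Keep the cumulative DB+OLE display on the safety set.
- **Appendix 2.1:** exclude post-treatment follow-up values of participants without an open-label dose from the Week 20 and later windows.
- **SAP 6.4.2:** add the number entering the OLE, which the disposition list lacks.

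The cost is SAP wording and one flag, from the switch date already derived from the dosing CRF; no new data are needed. The downside is that OLE-set rates are conditional on entry in both arms and leave out etrasimod-arm DB drop-outs. A footnote should say so.
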